5.4.3 UNSCHEDULED VISITS

An unscheduled visit is defined as an interim visit requested by the participant or investigator due to an unanticipated problem. Data recorded at these visits will be entered into the database. Only relevant and applicable unscheduled visit information will be included in the final report as deemed necessary by the lead investigator.

5.5 STUDY PROCEDURES

Table 3 summarizes the procedures at each visit. The order of procedures is described in sections 5.4.2.

Table 3: Summary of procedures to be conducted at scheduled visits

Procedure	Screening Visit 1	Dispense Visit 2	Follow-up Visit 3
Informed consent	X		
Participant demographics (age, sex, ethnicity)	X		
Contact lens history	X		
Medical history and medications	X		
Changes in medical history/ medications		X	X
HCVA (logMAR) (habitual Spectacles)	X		
OSDI questionnaire	X		
CLDEQ-8 questionnaire	X (habitual CL)		X (study CL)
Comfort, dryness, vision, handling ratings, comfortable & total CL wear time over last month	X (habitual CL)		X (study CL)
Non-invasive tear break-up time (Oculus K5M)	X		
Tear meniscus height (Oculus K5M)	X		
Tear osmolarity (TearLab)	X		
Meibomian gland score (MG evaluator)	X		
HCVA (logMAR) (Contact lenses)	X (habitual and study CL)	X (habitual and study CL)	X (study CL)
Biomicroscopy (incl. staining assessment)	X	X	X
Auto refraction/auto keratometry: horizontal and vertical K readings	X		
Subjective refraction	X		
Lens performance (fit, wettability, deposition)	X (habitual CL)	X (habitual and study CL)	X (study CL)
Review of compliance (CL wear, completion of home ratings)		X	X
Subjective at-home ratings provided	X	X	
Study lens fitting	X		
Study lens dispense		X	
Collection of unused study lenses			X
Study Exit			X

5.5.1 CASE HISTORY

Demographics:

Demographic information from the participant will be obtained, including age, sex and ethnicity.

Medical History:

At screening, information will be obtained from participants about the current medication, allergies, and any medical conditions. At visits 2 and 3 participants will be asked about changes in their medication or health.

Contact Lens History:

Information will be obtained from the participant about the current contact lens type (lens name, brand), lens power, lens wear days and use of artificial tears. Participants will be asked how many years of lens wear experience they have and how long they have been wearing DD lenses.

5.5.2 QUESTIONNAIRES AND SUBJECTIVE RATINGS

Questionnaires:

At the screening visit (Visit 1), participants will complete the OSDI questionnaire to reflect their dry eye symptoms.

At visits 1 and 3, participants will complete the CLDEQ-8 questionnaire, reporting their experience with their habitual and study contact lenses, respectively, over the past 2 weeks.

Subjective ratings:

Participants will be provided with subjective rating 0-100 questionnaires related to comfort, dryness, vision, lens handling and will be asked for times of lens insertion and removal and reasons for lens removal as well as onset of discomfort on that day and reason for lens removal. This questionnaire will be completed at home on Days 1, 3, 5 after visit 1 and on Days 1, 3, 5, 7, 21, 28 after visit 2. Participants will be instructed that they must wear the study lenses on the days where they are required to complete the ratings, and will be scheduled to return for their next visit.

The same questionnaire will be provided to the participants during visit 1 and 3 to reflect their overall 'typical day' experience over the previous month.

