5.1.2 RANDOMIZATION

There will be no randomization in this study.

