5.2.2 NUMBER OF PARTICIPANTS

Up to 60 participants may be screened using CORE records and advertising approved by the UW Office of Research Ethics. Approximately 43 participants will be dispensed / randomized with study products, with a target of number of 39 participants completing the study. Informed consent will be obtained for all participants prior to their enrolment in the study (Appendix 1).

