5.2.3 INCLUSION AND EXCLUSION CRITERIA

A person is eligible for inclusion in the study if he/she:

1. Is at least 17 years of age and has full legal capacity to volunteer;
2. Has read and signed an information consent letter;
3. Is willing and able to follow instructions and maintain the appointment schedule;
4. As per TFOS DEWS II², have dry eye symptoms (without CL wear) as determined by an OSDI score of ≥ 13 and at least **one** of the following:
 - a. Tear osmolarity $\geq 308\text{mOsm/L}$ or interocular difference $>8\text{ mOsm/L}$
 - b. Non-invasive tear breakup time of < 10 seconds in at least one eye
 - c. More than 5 spots of corneal staining OR > 9 conjunctival spots in at least one eye
5. Reports dryness while wearing DD CLs with CLDEQ-8 score ≥ 12 and $\leq 20^3$
6. Habitually wears soft spherical DD CLs with a power between +6.00D and -10.00D
7. Manifest spectacle cyl $\leq 1.00\text{DC}$ in either eye
8. BCVA $\leq 0.20\text{ log MAR}$ each eye with habitual & DT1
9. Acceptable fit with habitual & DT1
10. Willing to wear DT1 CLs at least 3 days per week and 6 hours per day throughout the study

A person will be excluded from the study if he/she:

1. Is participating in any concurrent clinical or research study;
2. Has any known active* ocular disease and/or infection;
3. Has a systemic condition that in the opinion of the investigator may affect a study outcome variable;
4. Is using any systemic or topical medications that in the opinion of the investigator may affect a study outcome variable;
5. Has known sensitivity to the diagnostic pharmaceuticals to be used in the study;
6. Is pregnant, lactating or planning a pregnancy at the time of enrolment (by self-report);

7. Is aphakic;
8. Has undergone refractive error surgery;
9. Has taken part in another clinical research study within the last 14 days;
10. Current habitual wearer of DT1
11. Any ocular and/or systemic conditions or concomitant medication to contraindicate contact lens wear or be expected to interfere with the primary outcome variables.

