5.4 SCHEDULED AND UNSCHEDULED VISITS

This study has a total of 3 study visits, including the screening visit.

Pre-screening:

Potential participants who show an interest in the study will be provided with more details about the study over the phone as well as in writing (Recruit 01 Recruitment email). Two prescreening questionnaires (Appendix 4 CLDEQ-8: Symptoms with lens wear and Appendix 5 OSDI: Dry-eye symptoms without lens wear) will be attached to the email script and sent to participants in the CORE database or to participants expressing an interest in the study. These completed questionnaires will be used to determine whether the subject is likely to meet the dry eye symptom eligibility criteria. If interested, potential participants can return both questionnaires to CORE, in order to determine whether they may generally be suitable for the study based on the severity of their dry eye symptoms. Participants meeting the dry eye symptom criteria, according to the questionnaires, will be invited to a screening visit where their full eligibility will be determined. Questionnaires completed prior to the consent procedure will not be included in the analysis, instead the questionnaires will be completed again during the Screening visit. Participants may also be accepted to participate in the study without previously completing the questionnaires, however in order to save time and to avoid screen failures due to insufficient symptoms, completing the questionnaires prior to the screening visit is preferred.

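### The Visit 1 CLDEQ-8 is both the entry filter (12 to 20) and the only habitual value in the non-primary CLDEQ-8 comparison, so regression to the mean of unknown size and direction is mixed into the lens effect

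*Combined protocol and SAP*

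**What the plan says.** Inclusion criterion 5 in section 5.2.3 reads "Reports dryness while wearing DD CLs with CLDEQ-8 score" of at least 12 and at most 20. Full eligibility is settled at Visit 1, where the CLDEQ-8 is completed for habitual lenses over the past two weeks (section 5.4.2).

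Section 5.5.2 and Table 3 place the questionnaire at two visits only: "At visits 1 and 3, participants will complete the CLDEQ-8 questionnaire, reporting their experience with their habitual and study contact lenses, respectively". The Visit 2 procedures include no CLDEQ-8, although participants arrive in their habitual lenses. Table 4 in section 11.1 compares the two scores with a 2-sided paired t-test and repeats the comparison by dry-eye subtype. Section 5.1.2 states: "There will be no randomization in this study".

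On recruitment, section 5.2.2 says "Up to 60 participants may be screened using CORE records and advertising approved by the UW Office of Research Ethics" and "Approximately 43 participants will be dispensed / randomized with study products, with a target of number of 39 participants completing the study". Section 5.4 describes an e-mailed pre-screen using the same questionnaire. It is encouraged ("in order to save time and to avoid screen failures due to insufficient symptoms, completing the questionnaires prior to the screening visit is preferred") but optional ("Participants may also be accepted to participate in the study without previously completing the questionnaires"). Its answers are set aside ("Questionnaires completed prior to the consent procedure will not be included in the analysis") and the questionnaire is repeated at screening.

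**The concern.** A single questionnaire score contains error. If people are admitted because that score falls in a band, the errors of those admitted do not average zero unless the source population is centred on the band. A later score is not selected in this way, so the group mean drifts back towards the source mean even if the new lens does nothing.

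Here the habitual value is truncated at 12 and 20 and the DT1 value is not. Everyone moves from habitual lenses to DT1 with no parallel group, and section 11.1 describes no adjustment, so the drift enters the paired difference as apparent lens effect. What is at stake is the interpretation of one non-primary comparison and its strata: a small CLDEQ-8 change could come partly or wholly from selection.

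**Working it through.** **The plan's own figure.** The sample size in section 5.2.1 reproduces. With diff/SD = 0.60 and two-sided alpha 0.05, the exact paired t-test (noncentral t) needs n = 39 for 95% power (power 0.9546). That calculation concerns the 0-100 subjective ratings, not the CLDEQ-8.

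**Inputs from the documents.** Band 12 to 20; up to 60 screened; about 43 dispensed; 39 completing; two-sided 5% test; CLDEQ-8 at Visits 1 and 3 only.

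**Inputs assumed, because the documents give none.** Source mean 10, 12, 14, 16 or 18; SD 5 or 6; retest correlation r = 0.7, 0.8 or 0.9 (30 scenarios); normal true score plus normal error; no lens effect. The source population is interested wearers before any pre-screen.

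**Direction, from a single gate at Visit 1.** Expected fall from Visit 1 to Visit 3 = (1 − r) × (mean of admitted scores − source mean), with continuity limits 11.5 and 20.5. For SD 6 and r = 0.8:

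- Source mean 12: admitted mean 15.31, fall 0.2 × 3.31 = 0.66 points, favouring DT1. The SD of the difference is 3.63, so the standardised shift is 0.66/3.63 = 0.18, and a paired t-test at n = 39 rejects about 20% of the time with no lens effect.
- Source mean 16: admitted mean 16.00, shift 0, rejection 5%.
- Source mean 18: admitted mean 16.35, fall 0.2 × (−1.65) = −0.33, against DT1, rejection about 9%.

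**Does a single gate fit the recruitment plan?** No. Without pre-screening, 36.1% to 63.2% of attendees pass the band, so 43/0.632 = 68 to 43/0.361 = 119 would have to be screened. The plan allows 60, which needs a pass rate of at least 43/60 = 72%. No effect size is claimed from the single-gate scenarios.

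**With everyone pre-screened** (earlier score also 12 to 20; 2 million draws per scenario; screened = 43 / pass rate at Visit 1 among those pre-screened), keeping only scenarios that need 60 or fewer:

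| Assumption | Scenarios that fit | Largest absolute shift | Highest false significance, n = 39 |
|---|---|---|---|
| Pre-screen and Visit 1 errors independent, no other losses | 20 of 30 (two almost exactly at 60) | about 0.4 points | 12% |
| Independent, other criteria remove 10% of attendees | 7 | about 0.2 points | 8% |
| Errors correlated at 0.5, no other losses | nearly all | about 1.2 points | 53% |

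In the first row, 17 of the 20 scenarios lie at 5% to 8%. The three largest need 57.5, 54.3 and 56.2 screened. Dividing each by 0.9 gives 63.9, 60.3 and 62.4, so all three drop out in the second row. The extreme in the third row is mean 10, SD 5, r = 0.7, with about 58 screened.

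In the strata, at an assumed 39/3 = 13 each, false significance is 5% to 7% under the first row's assumptions.

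**Not modelled.** The OSDI criterion, which could move the source mean, and repeat screenings (section 5.2.4).

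**The case against.** The strongest reply is that nothing important rests on this. The CLDEQ-8 is not a primary endpoint (section 2), is not in the hypothesis (section 4), and drives neither the sample size nor the equivalence/superiority evaluation. The band is two-sided and pre-screening is preferred, and both shrink the shift. Time and expectation effects already confound every habitual-versus-DT1 comparison in this openly uncontrolled design. The size rests wholly on assumed inputs. All of this stands, and it limits the weight of the point.

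It does not answer the structural fact. Pre-screening answers are not analysed, and the band is applied again to the score that is, so error in that score is still selected on. That overlap holds whatever the assumed inputs; only its size depends on them.

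A reader might infer more than the documents support:

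- *That the plan is biased in favour of DT1.* The sign depends on a source mean that the documents do not give.
- *That 0.4 points and 12% is an upper limit.* It is not. The figure moves both ways with the correlation between pre-screen and Visit 1 errors and with losses on the other criteria. The interval between pre-screening and Visit 1 is not stated.
- *That the primary ratings are affected in the same way.* They are not entry filters. They may correlate with the CLDEQ-8, but the documents give nothing from which to size that, and it is not part of this point.

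**Conclusion.** The concern holds as a minor design point. One score serves as entry gate and as the only habitual value in the Table 4 CLDEQ-8 comparison and its strata, so a selection shift cannot be separated from a lens effect there.

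Size and direction cannot be fixed from the documents. With a source mean of 10-18, SD 5-6, retest correlation 0.7-0.9, n = 39, everyone pre-screened and 60 or fewer screened, the absolute shift is about 0 to 0.4 points with 5% to 12% false significance if pre-screen and Visit 1 errors are independent. It is at most about 0.2 points and 8% if other criteria also remove 10% of attendees. It reaches about 1.2 points and 53% if those errors correlate at 0.5 and no other criterion removes anyone. None of these is a ceiling. The primary endpoints, the sample size of 39 and the equivalence/superiority evaluation do not use the CLDEQ-8 and are unaffected.

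**What to change.** Give the CLDEQ-8 again at Visit 2, referring to habitual lenses, before DT1 is dispensed. Use that score as the habitual value in the Table 4 CLDEQ-8 comparison and its dry-eye-subtype strata, and keep the Visit 1 score for eligibility only. Update Table 3 and sections 5.4.2 and 5.5.2 to match, and name the Visit 2 score in Table 4. This reduces the shift whichever way it runs.

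Costs and limits:

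- One extra 8-item questionnaire at an existing visit, plus protocol and CRF wording.
- Visit 2 falls 6 to 14 days after Visit 1. With two-week recall, the periods overlap by up to 14 − 6 = 8 of 14 days, so the shift is reduced, not eliminated. If Visit 1 and Visit 2 errors correlate at 0.5 (assumed), about half remains: roughly 0.2 of 0.4 points, or 0.6 of 1.2.
- The SD of the paired difference rises by about 4% to 9% if the errors are independent, in the 20 scenarios that fit.
- Time and expectation effects of the uncontrolled design remain, so the change does not by itself isolate a lens effect.

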5.5.3 VISUAL ACUITY

Visual acuity will be measured using high contrast computer-generated acuity charts.

Participants will be asked to read letters that progressively decrease in size on a computer screen located at a distance of 6 meters. Measurements will be taken during the subjective refraction, with habitual lenses, study lenses and habitual spectacles.

5.5.4 AUTOREFRACTION

Participants will be asked to focus on a target while seated at an instrument that measures their approximate spectacle prescription and corneal shape.

5.5.5 SUBJECTIVE REFRACTION

Participants will be asked to read a letter chart from a distance through lenses placed in front of their eyes. They will also be asked to compare clarity of your vision between different lenses placed in front of your eyes. This procedure aids to determine their spectacle and/or contact lens prescription.

5.5.6 NON-INVASIVE BREAK-UP TIME

The participant will be seated in front of a device (OCULUS Keratograph (K5M) that will project rings of light (Placido discs) onto the tear film. The participant will be asked to keep their eyes open for as long as they can and the time until the rings first begin to distort or break will be recorded. Three measurements will be taken for each eye to obtain an average value.

5.5.7 TEAR MENISCUS HEIGHT

The participant will be seated in front of the OCULUS Keratograph (K5M) with their chin on the chin rest and head against the forehead rest. The investigator will select the Tear meniscus height feature and will take images of the ocular surface of each eye.

5.5.8 TEAR OSMOMETRY

The participant will be asked to lean their head back and gaze towards the ceiling. The TearLab™ pens are loaded with sterile test cards. The pen will be used to gather ~50nL of tears

from one eye at a time, from the lower lateral tear meniscus without making direct contact with the eye. The pen will be docked to the base instrument to determine tear osmolarity.

5.5.9 LENS PERFORMANCE

Contact lens fit:

Lens fit will be assessed to ensure acceptable lens fit with a participant's habitual and study lenses using a 0-4 scale, (0= perfect lens fit).

Contact lens wettability and deposits:

Contact lens wettability and deposits will be graded with participant's habitual and study lenses using e.g. 32x magnification, on a 0-4 scale, 0 = excellent wettability, 0= no deposits.

5.5.10 SLIT LAMP BIOMICROSCOPY

The participant will be seated behind a slit lamp and the following will be assessed:

Cornea:

Any current or past corneal observations (such as infiltrates, old scars, etc) will be documented at each visit.

Corneal and conjunctival staining:

A sodium fluorescein strip, wetted with a few drops of saline, will be applied to the superior bulbar conjunctiva of both eyes. Staining will be graded using the Efron grading scale (0 to 4, 0 = normal) in 0.1 scale increments, while viewing with cobalt blue light through a Wratten no. 12 barrier filter.

Bulbar and limbal hyperemia:

Ocular redness will be assessed for the bulbar and limbal conjunctiva using the EFRON grading scale (0 to 4, 0 = normal; 0.1 increments). Redness will also objectively be assessed using an imaging technique provided by the Oculus K5M.

Palpebral conjunctival hyperemia and roughness:

The redness and roughness of the upper and lower eyelids (tarsal plate zone 2) will be assessed using the Efron grading scale (0 to 4, 0 = normal/ uniform satin appearance).

5.5.11 MEIBOMIAN GLAND EXPRESSIBILITY

Meibomian gland dysfunction results in stagnation of the meibum (oil) within the glands. The ease of expression of the gland and the quality of the expressed contents therefore provides an indication of the functional capabilities of the glands. The MG Evaluator (TearScience/J&J) will be used to apply a pressure of 1.2g/mm^2 to the lower eyelid just inferior to the lid margin in three areas – nasal, central and temporal. Five consecutive glands in each area will be assessed for expressibility. Glands will be graded as follows: 0: blocked, 1: inspissated (toothpaste), 2: cloudy with debris, 3: clear, the results for each location will be summed (Meibomian gland score).

5.5.12 MEIBOGRAPHY

While seated at the Lipiview II instrument the participant will be asked to place their chin on the chin rest and head against the forehead rest. The lower lid will be everted and infrared images will be taken of the exposed palpebral surface. This will be repeated for the superior eyelid. The grading of meibomian gland dropout will be conducted on the images after all participants are completed. The grading scale used will be the one described by Arita et al.⁴ the Meiboscore, where: Grade 0: no dropout, Grade 1: $< 1/3$ total area dropout, Grade 2: $1/3$ to $2/3$ total area dropout, Grade 3: $> 2/3$ total area dropout.

6 MONITORING PROTOCOL ADHERENCE

All personnel involved in this study will be listed on a delegation log and their training will be documented. Consent documentation will be reviewed by personnel not involved in the consent process. Visit windows will be reviewed when determining the analysis cohort. All adverse events and protocol deviations will be reviewed by the Lead Investigator. Serious adverse events and major protocol deviations will be reviewed by the Principal Investigator.

7 POTENTIAL RISKS AND BENEFITS TO HUMAN PARTICIPANTS

This is a minimal risk study because of the use of marketed products and standard optometric assessments.

Contact lenses in this study will be worn on a daily wear (and daily disposable) basis. Adverse events and/ or complications in daily wear of soft contact lenses can occur (e.g. inflammation and infection). Complications that may occur during the wearing of contact lenses include discomfort, dryness, aching or itching eyes, excessive tearing, discharge, hyperemia and variable or blurred vision. More serious risks may include photophobia, iritis, corneal edema or eye infection. Although contact lens-related infections are very infrequent, the possibility does exist. The

incidence of infection due to daily-wear soft lenses is 0.035%. Almost always an infection will occur only in one eye. Thirty five million Americans who currently wear contact lenses assume this risk.

When contact lenses are worn on a daily wear basis there is a small risk of an adverse event compared to not wearing contact lenses. When contact lenses are worn on an extended wear basis, there is a significantly increased risk of an adverse reaction compared with wearing contact lenses on a daily wear basis.

A dye (fluorescein) normally used for eye exams is being used in this study. Although rare, it is possible that participants may have an allergic reaction to the dye. This could cause discomfort to their eye.

Participants are advised to inform the investigator of any sensitivities to any ophthalmic drops or study products.

Additionally, it is possible that participants may experience temporary discomfort associated with the study procedures /products including: burning and stinging, blurred vision, sandiness or grittiness, light sensitivity, dryness, itching, crusty eyes and foreign body sensation.

The study lens may provide fewer signs and symptoms of dry eye during wear, however, there is no guarantee that participants will benefit from participating in this study. In addition, participants will have the opportunity to try a different type of soft contact lenses at no cost to them.

Participation in this study may contribute to scientific research information that may be used in the development of new contact lens products. Information from this study may help researchers and the funding company to better understand if the use of specific daily disposable lens types in lens wearers with dry eye disease.

